2.2 Study design

A retrospective observational database study using the Optimum Patient Care Research Database. The data utilised in this study ranges from 1997 – 2013. Eligible patients must have a minimum of one year of data prior to their initial date of COPD diagnosis for baseline period, and a minimum of two years of data post their initial COPD diagnosis for outcome period to assess patient characteristics and pharmacological treatment prescriptions.

Cohorts will be chosen to assess how prescription patterns have changed over time and if certain factors such as the introduction of QoF1 in 2004 and Tiotropium (LAMA) becoming licensed in UK in January 2002 influence prescribing behaviour.

Patients will be split into three cohorts based on their date of initial COPD diagnosis:

- 1997 – 2001
- 2002 – 2006
- 2007 – 2010

COPD initial therapy will be defined as pharmacological therapy prescribed during one year prior to and at the initial date of COPD diagnosis (baseline period). COPD therapies will be grouped by treatment class:

- Inhaled corticosteroid (ICS),
- long-acting β_2 -agonist (LABA),
- long-acting muscarinic antagonist (LAMA),
- short-acting β_2 -agonist (SABA),
- short-acting muscarinic antagonist (SAMA) (in single, dual or triple therapy)
- Other respiratory pharmacological therapies (theophylline)
- None (no prior baseline pharmacological therapy).

To identify possible drivers of treatment choice, analyses will be conducted in subgroups according to:

- Year of initial COPD diagnosis
- Comorbid asthma diagnosis
- Lung function grade (GOLD stage 1, 2, 3 or 4 [2])
- mMRC dyspnea scale score
- Baseline exacerbation rate.

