5.4 Analysis of study outcomes

COPD initial treatment patterns

Logistic regression analysis for all patients receiving first COPD therapy. This analysis will be conducted on:

- a. All patients receiving first COPD therapy
- b. The subgroup of patients who receive their first therapy on their date of COPD diagnosis

This will be carried out as follows:

Investigate the COPD therapy distribution of by the following main potential predictors:

- a. Year of initial COPD diagnosis (1997-2001; 2002-2006; 2007-2010)
- b. Presence of co-morbid asthma diagnosis
- c. Lung function grade (please note that GOLD stage 2 will be used as the reference). This will also be repeated for the earlier analysis investigating predictors of initial therapy choice for all patients receiving first COPD therapy
- d. mMRC score
- e. Annual exacerbation rates
- f. GOLD group with the following comparisons:
 - B vs A
 - D vs C
 - A+B vs C+D

For each potential predictor consider:

- the distribution of initial COPD therapy (number and percentage of patients and bar chart) will be summarised
- Need to test to see if it varies among the categories of each potential predictor with a chi-square.

Predictors of initial COPD treatment

Evaluate how the potential predictors outlined above could affect the choice of initial COPD therapy in terms of:

a. Odds of being prescribed any initial COPD therapy vs. no therapy

For each potential predictor:

- The distribution of initial COPD therapy (yes/no) (number and percentage of patients and bar chart) will be summarised and a test to see if it varies among the categories of each potential predictor with a chi-square will be completed.
- Odds ratios (ORs) with their 95% confidence intervals (CIs) will be calculated using an univariable logistic regression model and a multivariable logistic regression model with stepwise reduction to derive best-fitting model of non-collinear predictors
- Presence of co-morbid asthma diagnosis used both as adjustment and as stratification variable (two multivariable models)
- Collinearity analysis on all potential predictors and confounders

b. Odds of receiving initial COPD maintenance therapy vs. short-acting agents/no therapy

For each potential predictor:

- The distribution of initial COPD maintenance therapy (yes/no) (number and percentage of patients and bar chart) will be summarised and tested to see if it varies among the categories of each potential predictor with a chi-square.

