12.0 APPENDIX

12.1 Appendix 1: Definitions

Variable Name	Description	Time Period
Year of COPD diagnosis	Year of First COPD diagnosis	n/a
IDD Cohort	Year of first COPD diagnosis split into three cohorts: 1997 -2001, 2002 - 2006, 2007 - 2010	n/a
Age	Age at COPD diagnosis	n/a
Gender	Gender of patient: Male, Female	n/a
Smoking Status	Smoking status recorded in routine medical notes closest to date of COPD diagnosis	Closest to date of COPD diagnosis
Body Mass Index (BMI)	BMI defined as: Underweight = < 18.499, Normal = $\geq 18.50 - 24.99$, Overweight = ≥ 25.00 , Obese = ≥ 30.00	Closest to date of COPD diagnosis
Exacerbation Rate	Exacerbations were defined as: (i) COPD-related hospital admissions or Emergency Department attendance; (ii) use of acute oral steroids; (iii) General practitioner consultations for lower respiratory tract infections. Two exacerbations occurring within 2 weeks of one another were counted only once.	Calculated during the year prior to and including the date of COPD diagnosis.
mMRC Score	mMRC scores were based on the 5-point 162 scale of the British Medical Research Council questionnaire assessing perceived breathlessness. Combined mMRC score from either routine medical notes or questionnaire data if available.	Closest to date of COPD diagnosis
Lung Function Group	Lung function grade was calculated using GOLD Stage 1, 2, 3 and 4 criteria	Closest to date of COPD diagnosis
Asthma Diagnosis	Presence / absence of a co-morbid diagnosis of Asthma in routine medical notes	Closest to date of COPD diagnosis
Rhinitis Diagnosis	Presence / absence of a co-morbid diagnosis of Rhinitis in routine medical notes	Closest to date of COPD diagnosis
Gastroesophageal reflux disease (GERD)	Presence / absence of a co-morbid diagnosis of GERD in routine medical notes	Closest to date of COPD diagnosis
Heart Failure	Presence / absence of a co-morbid diagnosis of Heart Failure in routine medical notes	Closest to date of COPD diagnosis
Chronic Kidney Disease	Presence / absence of a co-morbid diagnosis of Chronic Kidney Disease in routine medical notes	Closest to date of COPD diagnosis
Osteoporosis	Presence / absence of a co-morbid diagnosis of Osteoporosis in routine medical notes	Closest to date of COPD diagnosis

Diabetes	Presence / absence of a co-morbid diagnosis of Diabetes in routine medical notes	Closest to date of COPD diagnosis

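### The three diagnosis cohorts cannot separate an effect of the January 2002 tiotropium licence from steady drift, and no cohort contrast isolates the 2004 QoF introduction, although section 2.2 gives both as reasons for choosing the cohorts

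*Protocol*

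**What the plan says.** Section 2.2 (Study design) gives two reasons for the cohorts in one sentence. It opens: "Cohorts will be chosen to assess how prescription patterns have changed over time and if certain factors such as the introduction of QoF1 in 2004". The second event that this sentence names is the licence: "Tiotropium (LAMA) becoming licensed in UK in January 2002 influence prescribing behaviour". It then fixes the time scale: "Patients will be split into three cohorts based on their date of initial COPD diagnosis", namely 1997-2001, 2002-2006 and 2007-2010.

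Section 5.4 carries the same blocks into the analysis as "Year of initial COPD diagnosis (1997-2001; 2002-2006; 2007-2010" (bracket closed in the original). For the therapy distribution it says: "Need to test to see if it varies among the categories of each potential predictor with a chi-square". For both outcomes (any therapy, and maintenance therapy) it then plans a univariable logistic model and "a multivariable logistic regression model with stepwise reduction to derive best-fitting model of non-collinear predictors". It names no linear calendar term, step, change of slope or unaffected comparison series. Mock Table 3 in Appendix 3 uses the same three levels.

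Appendix 1 defines a separate variable, "Year of First COPD diagnosis", next to the cohort variable. Section 5.4 gives no model that uses it ungrouped. The trends in section 5.2 are p-values between 0.05 and 0.10, not trends over time.

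**The concern.** A block contrast asks whether later patients differ from earlier ones. Section 2.2 asks something narrower: whether prescribing changed because of something that happened in January 2002 or in 2004. If prescribing was already drifting from 1997, adjacent blocks differ even when neither event did anything.

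The two events fail in different ways. January 2002 sits on a block boundary, so a contrast straddles it, but that contrast mixes any licence effect with drift. The year 2004 sits inside the middle block, so no planned contrast tests QoF, with or without drift.

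What is at stake is the reading of the cohort odds ratios. The design section offers the events as their explanation, and the stated analysis cannot support that explanation.

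**Working it through.** **Inputs from the protocol.** Block limits and event dates come from section 2.2, and the 0.05 level from section 5.2 (taken as two-sided). The protocol states no sample size, treated share or expected drift, so there is no figure of its own to reproduce.

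**Assumed inputs.** 60% treated in 1997; constant annual OR of 1.05 to 2010; no step anywhere; equal numbers per diagnosis year, either 200 (14 × 200 = 2,800 in all) or 580 (14 × 580 = 8,120).

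**Expected block odds ratios.** logit(p) = log(1.5) + (year − 1997) × log(1.05). Averaging p within blocks gives 0.623, 0.678 and 0.724.

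- Odds: 0.623/0.377 = 1.653; 0.678/0.322 = 2.109; 0.724/0.276 = 2.627 (from unrounded shares).
- 2002-2006 versus 1997-2001: 2.109/1.653 = 1.28.
- 2007-2010 versus 2002-2006: 2.627/2.109 = 1.25.
- Cross-check: the block mid-years are 5 and 4.5 years apart, and 1.05^5 = 1.28 and 1.05^4.5 = 1.25.

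**Chance that the contrast straddling January 2002 is significant.** SE² = 1/[n₁p₁(1−p₁)] + 1/[n₂p₂(1−p₂)].

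- 200 per year (1,000 per block): SE = 0.094; z = log(1.276)/0.094 = 2.59; probability Φ(2.59 − 1.96) = 0.74. Simulation gives 0.73.
- 580 per year (2,900 per block): SE = 0.055; z = 4.41; probability 0.99. Simulation gives 0.995.

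**Range.** Annual ORs of 1.03 and 1.08 give adjacent-block ORs of 1.16 and 1.14, and of 1.47 and 1.41. A second simulation (2,000 data sets per scenario, mid-period treated share 0.50 or 0.75, no step) gave these rates of significance for 2002-2006 versus 1997-2001:

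| Annual OR | N = 1,000 | N = 5,000 | N = 10,000 | N = 20,000 |
|---|---|---|---|---|
| 1.00 | 4-5% | 5% | 5-6% | 5% |
| 1.02 | 9% | 25-31% | 43-54% | 74-84% |
| 1.05 | 31-36% | 91-96% | over 99% | 100% |
| 1.10 | 82-88% | 100% | 100% | 100% |

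**QoF.** Two of the five diagnosis years in the middle block (2002 and 2003, 40%) precede 2004. The first contrast therefore mixes the licence, part of the QoF period and drift. The second compares a wholly later block with one that is itself mixed.

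**What a trend-plus-steps model does.** The model is logistic, with linear year and steps at 2002 and 2004.

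- Under linear log-odds drift and no step, each step is falsely significant in about 4-6% of simulations, and at least one of the two in about 8-10%.
- Under smooth drift that levels off or is S-shaped, again with no step, at least one is falsely significant in about 20-45%.
- The SE of the 2002 step log OR is about 0.15 at 200 per year and 0.09 at 580. A true step of OR 1.4 is found in 53% and 95% of simulations.
- If uptake is instead gradual, reaching OR 1.4 only by 2010 with no drift, the 2002 step is significant in only 6.5-8%.

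**The case against.** The strongest reply is that the protocol never promises to attribute a cohort OR to an event. The event question appears in one sentence about how the cohorts were chosen. That sentence's first purpose is change over time, which block contrasts do describe. The events are absent from the objectives, the primary outcome and section 5.4, and the example regression table (Table 4) has no diagnosis-period row. This stands. A reader might infer that drift would be reported as a licence or QoF effect, but no text says so. What remains is that section 2.2 poses the question and the protocol's only stated use of time cannot answer it.

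A statistical analysis plan, not shown here, could add a finer time model, since diagnosis year is already defined. That is possible. The point, however, concerns a purpose and a three-level predictor that the protocol itself fixes.

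The size depends on assumed drift and sample size. That is true, and with small drift and 1,000 patients the false signal is uncommon (9%). The inability to separate step from drift does not depend on either.

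A reader might also infer that trend left inside the blocks distorts the other predictors' odds ratios. The figures do not support that. For a predictor with no effect and 25% prevalence in 1997, with its prevalence and prescribing both drifting at an annual OR of 1.05, the spurious OR after block adjustment is 1.004. At 1.10 it is 1.017. This harm is negligible.

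Finally, a segmented model is no clean replacement, because its nominal error rate holds only if the trend has the assumed shape. This also stands and limits the remedy.

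**Conclusion.** The point holds in limited form. As planned, the 2002-2006 versus 1997-2001 contrast cannot distinguish a licence effect from steady drift, and no contrast isolates QoF. Under the assumed 60% treated in 1997 and annual OR of 1.05, drift alone gives an OR of 1.28, significant in about 73% of studies at 200 patients per year and about 100% at 580. The rate falls with weaker drift or fewer patients.

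The cohorts remain sound for describing change between periods, and the predictor analyses for asthma, lung function, breathlessness and exacerbations are not materially affected. It would go too far to say that the protocol commits to a false attribution, or that step terms would settle the question. The correction is worth making because it is cheap and limits what may be concluded from the cohort odds ratios.

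**What to change.** **Wording, needed in any case.** State in sections 2.2 and 5.4 that cohort odds ratios describe change over time and will not be attributed to the tiotropium licence or to QoF. If nothing more is wanted, remove the event question from section 2.2.

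**If the event question is kept.** For each of the two outcomes, add one supporting logistic model using the diagnosis year already defined in Appendix 1 (or month, if available). Include an underlying trend and change terms at January 2002 and at the 2004 QoF introduction. Specify in advance:

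- a check against non-linear trend forms;
- how the change terms allow for the one-year look-back. Section 2.2 counts therapy from one year before diagnosis, so patients diagnosed during 2002 have windows that straddle the licence date, and the same happens around QoF;
- that the change terms are reported as suggestive only.

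**Cost.** A wording change and at most one extra model per outcome, with no new data if year is used. Intervals are wider (SE of the 2002 step log OR about 0.09-0.15 at the assumed sizes). Results are sensitive to the trend shape, with at least one false step in about 20-45% of simulations under smooth non-linear drift. Only 2002 and 2003 lie between the two dates, so the data say little about separate changes there.

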4.2 Primary outcome

Predictors of initial treatment patterns

Primary outcome will identify predictors of GP prescribing behaviour when treating newly diagnosed COPD patients with their first pharmacological therapy. It will assess the odds of being prescribed:

- any initial COPD therapy vs.
- no COPD therapy

A further analysis will be conducted in regard to the odds of being prescribed:

- maintenance therapy versus
- short-acting agents/no therapy

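### Initial therapy is defined over a whole year, but the outcome is the first therapy; as written, later step-up in that year counts as initial maintenance therapy

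*Protocol*

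**What the plan says.** Protocol section 2.2 gives the only operational definition: "COPD initial therapy will be defined as pharmacological therapy prescribed during one year prior to and at the initial date of COPD diagnosis". Treatments are then grouped by class, "in single, dual or triple therapy", and the untreated category is "None (no prior baseline pharmacological therapy", so that category describes the whole year. The section does not say how to class a patient who had several regimens in the year, or whether combined classes must be prescribed together.

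Section 4.2 describes the target differently. It concerns GP behaviour "when treating newly diagnosed COPD patients with their first pharmacological therapy". Section 5.4 also speaks of first therapy: analysis (a) covers "all patients receiving first COPD therapy", and analysis (b) covers "The subgroup of patients who receive their first therapy on their date of COPD diagnosis". Two contrasts are modelled: "Odds of being prescribed any initial COPD therapy vs. no therapy" and "Odds of receiving initial COPD maintenance therapy vs. short-acting agents/no therapy".

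Appendix 1 (Definitions) is captioned as the full variable list but has no entry for initial or maintenance therapy. It counts exacerbations over the year up to and including diagnosis, which is the same year as the therapy window.

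**The concern.** The document holds two notions of initial therapy, the whole year and the first regimen, and does not reconcile them. An analyst coding from section 2.2 and one coding from section 4.2 would build different variables.

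Under the section 2.2 wording, a patient given a short-acting agent early in the year and a maintenance agent months later falls in the maintenance group. A patient switched from one class to another can appear as dual therapy without ever having had both together. The maintenance outcome then mixes first choice with up to a year of step-up and switching, and the class distributions shift towards combinations.

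The shared 12-month period matters most. An exacerbation that follows the first prescription and prompts step-up would be read as a predictor of the initial choice, although it came after that choice. Maintenance versus short-acting or no therapy is one of the study's two stated comparisons.

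**Working it through.** The protocol gives no figure to reproduce on this point: no step-up rate, sample size or event count. The check is therefore a comparison of definitions followed by an illustration with assumed rates.

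**Definitions side by side**

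- Section 2.2: the therapy prescribed in the year up to and including diagnosis.
- Sections 4.2 and 5.4: the first therapy.
- The two agree for a patient with one unchanged regimen in the year. They can differ for anyone with an addition or a switch.

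**Effect on the maintenance contrast**

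Inputs, all assumed and identical in patients with and without exacerbations, so that the true odds ratio is 1.00:

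- *pm*: share whose first regimen is maintenance
- *ps*: share whose first regimen is short-acting
- the remainder is untreated

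The share *s* of short-acting starters stepped up within the window is *s0* without exacerbations and *s1* with them.

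Observed maintenance share: m = pm + ps × s.

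Odds ratio: [m1/(1 − m1)] / [m0/(1 − m0)].

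Worked case: pm = 0.40, ps = 0.40, s0 = 0.10, s1 = 0.30.

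- m0 = 0.40 + 0.40 × 0.10 = 0.44, odds 0.44/0.56 = 0.786
- m1 = 0.40 + 0.40 × 0.30 = 0.52, odds 0.52/0.48 = 1.083
- OR = 1.083/0.786 = 1.38

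| pm | ps | s0 | s1 | m0 | m1 | OR (true 1.00) |
|---|---|---|---|---|---|---|
| 0.40 | 0.35 | 0.05 | 0.05 | 0.4175 | 0.4175 | 1.00 |
| 0.40 | 0.35 | 0.05 | 0.10 | 0.4175 | 0.435 | 1.07 |
| 0.40 | 0.40 | 0.10 | 0.20 | 0.44 | 0.48 | 1.17 |
| 0.40 | 0.35 | 0.05 | 0.20 | 0.4175 | 0.47 | 1.24 |
| 0.40 | 0.35 | 0.10 | 0.30 | 0.435 | 0.505 | 1.33 |
| 0.40 | 0.40 | 0.10 | 0.30 | 0.44 | 0.52 | 1.38 |
| 0.30 | 0.50 | 0.10 | 0.30 | 0.35 | 0.45 | 1.52 |
| 0.40 | 0.40 | 0.10 | 0.40 | 0.44 | 0.56 | 1.62 |

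With equal step-up the odds ratio is unbiased here, but the maintenance share is still overstated (0.4175 against 0.40).

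**Any therapy versus none**

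The treated share is pm + ps, which does not contain *s*. A short-acting starter is treated before and after step-up, so this contrast does not move in any row.

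**Subgroup (b)**

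The window closes on the diagnosis date. A patient whose first therapy falls on that date has no later time inside the window in which to be stepped up or switched.

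**The case against.** The strongest reply is that the protocol nowhere says prescriptions are pooled. Section 2.2 does not state that stepped-up patients are classed as maintenance, its mention of dual and triple therapy could mean concurrent regimens, and sections 4.2 and 5.4 point to a first-therapy intent. Subgroup (b) cannot even be formed without dating the first therapy. Assigning one class to a patient with several prescriptions might also be left to a SAP, which is not at hand.

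Part of this stands. A reader might infer a deliberate pooling rule, and the text does not support that. Pooling is what results from applying section 2.2 literally. The point still goes beyond missing detail, because the protocol fixes a definition that differs from its own outcome.

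A second reply concerns the remedy. Nothing in sections 2.2 or 3.1 requires patients to be untreated before the window. For someone already on repeat prescriptions, the first prescribing date in the window is simply whichever repeat fell first. Suppose such a patient uses a short-acting agent and a maintenance agent on independent, uniformly offset cycles of T days. The chance that the short-acting item comes first and the other follows more than 14 days later is 0.5 × ((T − 14)/T)²: 14% for T = 30 and 29% for T = 60. Synchronised repeats would lower this. The reply stands in full, and the first-regimen rule must be restricted accordingly.

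**Conclusion.** The concern holds in a limited form. The section 2.2 definition conflicts with sections 4.2 and 5.4 and, applied as written, misclassifies patients who are stepped up or switched within the year. What is exposed is the maintenance contrast in analysis (a) and the single, dual and triple distributions.

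Inflation of the exacerbation odds ratios is conditional on step-up being commoner after exacerbations. Under the assumed rates a true value of 1.00 appears as about 1.07 to 1.62; with equal step-up it stays 1.00. The direction follows from that condition. The size rests wholly on assumed rates, because the protocol gives none.

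Three stronger readings are not supported:

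- The whole primary outcome is not contaminated, since any-versus-none cannot change through step-up.
- The plan is not without a safeguard, since subgroup (b) largely avoids the problem. It is only a subgroup, however, and leaves (a) exposed.
- Inflation of the breathlessness (mMRC) odds ratios has not been shown. That score is taken closest to diagnosis, and the calculation above does not cover it.

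The correction is cheap and should be made before the outcome variable is derived.

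**What to change.** State one analytic rule in section 2.2, add it to Appendix 1, and use it in sections 4.2 and 5.4:

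- Assign class from the regimen on the earliest prescribing date. Count items issued the same day, or within a short fixed interval (14 days, for example), as concurrent.
- Report later additions separately as step-up.
- Apply the rule only to patients with no respiratory prescription on record before that date. Flag patients already on repeat therapy when the window opens and analyse them separately.
- Use this variable for the maintenance contrast and the class distributions. Any-versus-none needs no change on this account.
- Vary the co-prescription interval in a sensitivity analysis, and report subgroup (b) alongside (a) as a check.

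The cost is a derived variable, a flag and some wording, built from prescription dates that subgroup (b) already requires. The interval is a convention, so some true combinations issued later will be missed, and the first-therapy analysis set will be smaller. Section 3.1 asks for only one year of data before diagnosis. For patients with just that minimum, treatment before the window cannot be seen, and the report should say so.

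### Initial COPD therapy is measured up to the diagnosis date, but the stated question is what GPs first prescribe once COPD has been diagnosed

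*Protocol*

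**What the plan says.** Section 2.2 of the protocol takes initial therapy to be "pharmacological therapy prescribed during one year prior to and at the initial date of COPD diagnosis (baseline period". In the list that follows, the untreated category is "None (no prior baseline pharmacological therapy". Drugs are assigned by class only: "COPD therapies will be grouped by treatment class", with no condition on why they were prescribed.

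The target is worded differently. Section 2.1 speaks of prescribing for newly diagnosed patients. Section 4.2 wants "predictors of GP prescribing behaviour when treating newly diagnosed COPD patients with their first pharmacological therapy". It then sets two contrasts: any therapy against none, and maintenance therapy against short-acting agents or none.

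Section 2.2 also requires "a minimum of two years of data post their initial COPD diagnosis for outcome period to assess patient characteristics and pharmacological treatment prescriptions".

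Asthma is not an exclusion in section 3.1. Section 5.4 handles it as follows: "Presence of co-morbid asthma diagnosis used both as adjustment and as stratification variable (two multivariable models". The same section runs the regression in all patients receiving first therapy and again in the subgroup whose first therapy falls on the diagnosis date.

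**The concern.** The outcome window opens a year before the decision under study and closes on the day it is made. Two errors of classification follow.

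- A prescription written before anyone had diagnosed COPD counts as the GP's choice of COPD treatment. Because class alone decides, and patients with asthma are eligible, this includes inhalers given for asthma.
- A patient whose first prescription comes the day or the week after diagnosis is counted as untreated. In the second contrast, a patient whose maintenance inhaler starts after the diagnosis day falls in the comparison group.

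Both contrasts in section 4.2 rest on this one definition, and covariate adjustment does not correct an outcome taken from the wrong period. At stake is whether the ORs can be read as predictors of treatment choice at diagnosis. The asthma OR is the most exposed, because asthma is itself a reason for earlier inhaler use.

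**Working it through.** The protocol gives no treatment rates, sample size or event counts, so there is no figure of its own to reproduce. The timing comes from the text. The sizes below are illustrations on assumed rates.

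**Step 1: the periods side by side.**

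| Element | Period | Protocol |
|---|---|---|
| Initial therapy | year before diagnosis, up to and including the diagnosis date | 2.2 |
| Untreated category | no therapy in that same period | 2.2 |
| Stated target | first therapy once newly diagnosed | 2.1, 4.2 |
| Named outcome period | at least two years after diagnosis | 2.2 |

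No analysis listed in section 5.4 uses the named outcome period to classify initial therapy.

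**Step 2: prior prescribing counted as the outcome.** Assume that asthma has no effect on the decision at diagnosis (true OR 1). Let p_prior be the share with a respiratory prescription in the year before diagnosis. Let p_dx be the share of those not yet treated who start on the diagnosis day, equal in both groups. Then

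P(any) = p_prior + (1 − p_prior) × p_dx,

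and the OR is the ratio of the odds of P(any), asthma to no asthma.

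| Prior use, asthma vs none | p_dx | P(any) | Apparent OR |
|---|---|---|---|
| 50% vs 50% | 0.3 | 0.65 vs 0.65 | 1.00 |
| 60% vs 40% | 0.6 | 0.84 vs 0.76 | 1.66 |
| 60% vs 40% | 0.4 | 0.76 vs 0.64 | 1.78 |
| 60% vs 30% | 0.3 | 0.72 vs 0.51 | 2.47 |
| 80% vs 50% | 0.1 | 0.82 vs 0.55 | 3.73 |
| 80% vs 20% | 0.6 | 0.92 vs 0.68 | 5.41 |
| 80% vs 20% | 0.4 | 0.88 vs 0.52 | 6.77 |

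For example, 60% vs 40% with p_dx = 0.6 gives (0.84/0.16)/(0.76/0.24) = 5.25/3.17 = 1.66. With equal prior use the OR is 1, so the distortion comes entirely from the difference in prior prescribing.

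**Step 3: later starts counted as untreated.** Assume that 60% of the reference group are treated by shortly after diagnosis, and that a predictor has a true OR of 2. The odds are 1.5 and 3.0, so the shares treated are 0.60 and 0.75. Let a fraction f of treated patients start after the diagnosis day, equal in both groups. The observed shares are 0.60(1 − f) and 0.75(1 − f).

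| f | Observed shares | Observed OR |
|---|---|---|
| 10% | 0.675 vs 0.540 | 1.77 |
| 30% | 0.525 vs 0.420 | 1.53 |
| 50% | 0.375 vs 0.300 | 1.40 |

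Under the same assumption, a true OR of 1 stays at 1.

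**The case against.** The definition is explicit and openly labelled a baseline period, so it may be a deliberate choice in a descriptive study. Section 5.4 also contains two safeguards.

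- **The diagnosis-date subgroup.** It addresses prior prescribing directly. One could object that, as worded, it holds only treated patients. The all-patients set is worded the same way, so if untreated comparators are implied in one they are implied in the other. On that fair reading the subgroup does remove earlier prescribing. It remains a subgroup, however, and its untreated comparators still include everyone who started after the diagnosis day.
- **Adjustment and stratification for asthma.** These keep differences in asthma prescribing from driving the ORs of other predictors. It would therefore be too strong to say that asthma prescribing distorts every OR. The asthma OR in the all-patients analysis stays exposed, and the ORs within each stratum still use the mistimed outcome.

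Three stronger readings are tempting, and the protocol does not support them.

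- A reader might infer that the outcome mostly measures earlier prescribing, or that the asthma OR is nearly tautological. No rates are given, and a moderate gap in prior use yields only 1.66 to 1.78.
- The asthma OR of 3.88 in Table 4 of Appendix 3 might be taken as confirmation. That table is labelled an example and is not evidence.
- The two years after diagnosis might seem to serve no purpose. Section 3.1 takes spirometry from a five-year window around diagnosis, and Appendix 1 takes several variables closest to diagnosis, so some values may come from those years. Only their non-use in classifying initial therapy is established.

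**Conclusion.** The point holds. The therapy window in section 2.2 does not match the question in sections 2.1 and 4.2, and the safeguards in section 5.4 repair it only in part. This definition is stated in the protocol, so it is not a detail left to a later analysis plan.

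The direction of the asthma distortion is clear if patients with asthma have more prior inhaler use. Its size is not known: a true OR of 1 would appear as about 1.7 at 60% versus 40% prior use, and as 5 or more at 80% versus 20%. Separately, late starts would reduce a true OR of 2 to about 1.8 if 10% of treated patients start late, and to 1.4 if 50% do, provided that the late share is the same at each level of the predictor. All of these rates are assumptions.

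**What to change.** Define the primary outcome as the first COPD-class prescription on the diagnosis date or within a fixed, pre-specified window after it, among patients with no such prescription in the baseline year before diagnosis. The sponsor should choose the length of the window and vary it in sensitivity analysis. Report patients treated before diagnosis as a separate group, and keep the present definition as a sensitivity analysis.

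If the present window is intended, reword the aim, section 4.2 and the conclusions as predictors of therapy received up to diagnosis, and state that later starters count as untreated.

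The cost is protocol wording and re-coding. Section 3.1 already requires two years of data after diagnosis, so any window within that period is observed for every eligible patient. There are two downsides. The primary model becomes smaller and describes a narrower population, since previously treated patients leave it. A one-year period without treatment makes it more credible that the therapy was the first, but does not prove it.
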